**Funder**

This study is funded by Innovate UK.

This protocol describes the study and provides information about procedures for entering participants. Every care was taken in its drafting, but corrections or amendments may be necessary. These will be circulated to investigators in the study. Problems relating to this study should be referred, in the first instance, to the Chief Investigator.

This study will adhere to the principles outlined in the **UK Policy Frame Work for Health and Social Care Research**. It will be conducted in compliance with the protocol, the Data Protection Act and other regulatory requirements as appropriate.

**GLOSSARY OF ABBREVIATION**

AI	Artificial intelligence
ECG	Electrocardiogram
EPS	Electrophysiology study
PPG	Photoplethysmography
HCP	Healthcare professional

STUDY SUMMARY

TITLE	AI-ECG Accessory Pathway Localisation Study
DESIGN	Prospective validation study
AIMS	
 
1) To develop and finalise a machine learning algorithm to localise accessory pathways from the 12-lead ECG.
 
2) To prospectively validate machine learning algorithms for accessory pathway localisation through a clinical trial.
 

OUTCOME MEASURES	
 
• Key deliverable: A prospectively validated AI algorithm for accessory pathway localisation, which can produce reliable, reproducible and accurate outputs
 
• Outcome measures: 
 
• Overall accuracy of the AI algorithm predictions, as compared to the operator assessment.
 
• Overall accuracy of the AI algorithm predictions, as compared to the ground truth of successful ablation location determined by fluoroscopy <math>\pm</math> 3D mapping.
 
• Sensitivity, specificity, positive and negative predictive values, and F1 score of the ECG AI algorithm for accessory pathway localisation
 
• Difference in accuracy between the AI algorithm prediction and human estimation from the 12-lead ECG.
 
• Difference in accuracy between the AI algorithm and pre-specified, established manual localisation algorithms (Arruda, Milstein, Pambrun, Boersma, D'Avila and Chiang).
 
• Correlation of accessory pathway localisation by human estimation, and manual algorithm output as compared to the true location on 3D mapping.
 
 
 

POPULATION	Patients referred for an EPS
ELIGIBILITY	
Inclusion Criteria
 
 
1) Age 13 - 100 years old
 
2) Referred for invasive electrophysiological study as part of their usual clinical care
 
3) Manifest pre-excitation on their ECG any time prior to their procedure
 
4) Able to give consent
 
 
Exclusion criteria
 
 
1) Patients with known location of their accessory pathway from a previous EPS
 
2) Age <math><13</math> years old
 
3) Age <math>> 100</math> years old
 

DURATION	1 st March 2025 – 1 st March 2027

## 1. INTRODUCTION

### 1.1 BACKGROUND

Accessory pathways are congenital cardiac abnormalities that can enable electrical impulses to bypass normal atrioventricular nodal conduction. This leaves patients at risk of supraventricular tachycardias and even sudden death in the case of pre-excited atrial fibrillation. The location of an accessory pathway can be definitively established by successful ablation. It is desirable to localise a suspected accessory pathway prior to an invasive electrophysiological study both to guide procedure planning and to personalise the consent process: pathway location determines much of individual procedure risk.

Accessory pathway location can be estimated from the 12-lead ECG using either human expertise or manual localisation algorithms that rely on specific ECG features. These approaches are subject to inter-operator variability and are often time consuming and difficult to perform for inexperienced users, respectively. Validation studies of these algorithms have not shown high accuracy, or even reproducibility in some cases. These studies are also problematic due to being either retrospective, using strict eligibility criteria not representative of clinical practice, or validation cases being entirely non-external.

Artificial intelligence has been increasingly investigated for its role as a high-performance predictive tool in healthcare and beyond. Machine learning algorithms can reproducibly classify medical data with very high levels of accuracy. Within cardiology, AI has been successfully applied to ECG interpretation for several cardiac conditions. Our group has developed a proof-of-concept AI algorithm for accessory pathway localisation, which has demonstrated an accuracy of 93% when retrospectively applied to 156 12-lead ECGs (left vs septal vs right).

To formally validate the real-world accuracy of this AI algorithm for accessory pathway localisation, it is imperative that: 1. The algorithm is tested **prospectively**; 2. The algorithm is tested on **consecutive** cases, avoiding cherry-picking; 3. The tested algorithm is locked such that it cannot be influenced by any new data during testing. 4. The testing cohort must include **external** cases, to avoid AI overfitting and test generalisability. These standards are essential for robust validation and to provide a genuine assessment of the accuracy for the algorithm before real-world application and use in clinical practice.

## 2. STUDY OBJECTIVES

### Primary objectives

- 1) To finalise a testable ECG AI algorithm for accessory pathway localisation.
- 2) To prospectively validate the accuracy of the ECG AI algorithm for accessory pathway localisation, as compared to the ground truth of successful ablation location (determined by fluoroscopy  $\pm$  3D mapping) through a prospective clinical trial on consecutive unseen cases.

### Secondary objectives

- 1) To evaluate the relative performance of the AI algorithm compared to human interpretation and conventional manual algorithms.
- 2) To compare the accuracy of ground truth locations to complete annular maps from 3D electro-anatomical mapping.

### **3. STUDY DESIGN**

#### **3.1 RECRUITMENT**

We aim to recruit 100 patients for a prospective validation study of our AI algorithm for accessory pathway localisation. The direct care team will screen the records and identify patients followed up at Imperial College Healthcare Trust.

Patients will be contacted by members of their direct care team. This will occur either when they attend for routine appointments or during inpatient admission. The direct care team will obtain consent to share patients' information with the research care team. Once the patient has consented to their information being shared, a member of the research team will contact the patient and explain the details of the research study. The patient information leaflet will be provided to the patient via post or electronically via email with the patient's permission.

If the patient is agreeable, they will be formally consented on the day of their clinical EP study procedure by a member of the research team. Written consent will be gained prior to any data being collected or participation in the research protocol.

All patients recruited to this study must have had an ECG demonstrating manifest pre-excitation at any time prior to their EPS.

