#### **3.2 METHODOLOGY**

##### **Data collection**

All data will pseudonymised at the point of collection by the direct care team. Pseudonymised and anonymised data will be securely held password protected computers at Imperial College London (Sponsor). Pseudonymised data will be kept separately from the key that identifies it and separately from data with the patients name, hospital number, address and NHS number. With the consent of the patient and clinical care team medical information such as procedure reports will be obtained. These data will be kept separate from identifiable personal data. All identifiable information will be securely held in NHS Trust computers and will be held in strict compliance to NHS Data Protection and Confidentiality regulation. Patient identifiable information will not be shared from external institutions.

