##### **AI algorithm testing**

The AI algorithm has been trained using raw, digital 12-lead ECG data from patients with manifest accessory pathways who underwent successful ablation. The training data was labelled using associated procedure reports, fluoroscopy and electro-anatomical map data. The algorithm will output the location of an accessory pathway (left vs right, anterior vs posterior, septal vs lateral).

At commencement of the prospective validation study, the final AI accessory pathway localisation algorithm will be locked so that it cannot be trained on any new input data. This will be confirmed by an independent researcher. Using a digital 12-lead ECG as the input, the algorithm will output the categorical location of the pathway; this will be provided as a transverse axis location (left, septal, right) and a vertical axis location (anterior, mid, posterior).

Participants who agree to be recruited to the prospective validation study will undergo 12-lead ECG recordings via conventional digital ECG machines and EP recording systems during their EP study. These ECGs will be analysed at Imperial College London, where the AI algorithm will be applied to determine the AI-predicted location. At the time of their EP study, the successful ablation location will be recorded by the operating physician (estimated

from fluoroscopy). The proportion of ECGs correctly predicted by the AI algorithm, matching the operator assessment, will be the primary outcome measure of AI accuracy.

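### Does recruitment at one named trust break the protocol's own requirement for external test cases?

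*Protocol*

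**What the plan says.** Section 1.1 asks that the algorithm be tested prospectively, on consecutive cases, in locked form and on a cohort with external cases: "The testing cohort must include external cases, to avoid AI overfitting and test generalisability". Of all four it says "These standards are essential for robust validation and to provide a genuine assessment of the accuracy for the algorithm before real-world application". The same section faults earlier validation studies for having no external cases. It reports a pilot accuracy of 93% when the algorithm was "retrospectively applied to 156 12-lead ECGs", without saying where those ECGs came from.

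The later sections are less specific:

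- Section 2 sets two primary objectives. One is "To finalise a testable ECG AI algorithm for accessory pathway localisation". The other is validation "through a prospective clinical trial on consecutive unseen cases". The word external is not used.
- Section 3.1 plans 100 patients and says "The direct care team will screen the records and identify patients followed up at Imperial College Healthcare Trust". Section 4.1 refers to the research site in the singular.
- Section 3.2 (AI algorithm testing) says "The AI algorithm has been trained using raw, digital 12-lead ECG data from patients with manifest accessory pathways who underwent successful ablation". It gives the type of patient and the source of the labels, but no institution. The algorithm is locked when validation starts, and an independent researcher confirms this.
- Section 3.2 (Data collection) says "Patient identifiable information will not be shared from external institutions".
- Section 8.1 requires confirmation of capacity from each participating NHS trust. Section 8.5 assigns delegated responsibilities to trusts in the plural.

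**The concern.** Three of the four standards reappear in the operative sections: prospective and consecutive testing in section 2, and the lock in section 3.2. The fourth does not. No second recruiting trust is named, no number of external cases is set, and external is not defined.

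The natural meaning is a case from an institution that supplied no training data. If it meant only a case not used in training, it would add nothing, because any prospective case run through a locked algorithm is already unseen.

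Locking the algorithm and blinding the researcher who applies it prevent retraining on test data and biased reading. They do not show that the algorithm works where ECG equipment, patients or operators differ from those behind the training data. If the trial recruited at one trust and that trust also supplied the training ECGs, it could report a prospectively validated algorithm (section 3.4) while sharing the weakness that section 1.1 criticises in others.

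**Working it through.** The plan gives no figure for external cases, so there is none to reproduce. The check is of the text, followed by a count and one illustration of precision.

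**1. One trust or several?**

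| Statement | Points towards | Weight |
|---|---|---|
| 3.1: patients identified at one named trust | one trust | Study-specific, but does not say only |
| 4.1: the research site, singular | one trust | A single line; the next section carries a Study A label that matches nothing else in the protocol, so the wording here may be left over from a template |
| 3.2: external institutions and identifiable data | several | Study-specific, in the data-collection text |
| 5.2.2: local investigators | several | Standard governance wording |
| 8.1: each participating NHS trust | several | Standard governance wording |
| 8.5: NHS trusts taking part | several | Standard governance wording |

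The text is inconsistent on this. It does not establish a single-centre study. A site list may also stand on title or contact pages that are not in the text reviewed here.

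**2. When would the standard fail?** Take external to mean from a trust that supplied no training data, including any data used to finalise the algorithm before the lock. With 100 patients:

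- only the named trust recruits, and it supplied no training data: 100 of 100 external;
- only the named trust recruits, and it supplied training data: 0 of 100 external;
- several trusts recruit: the number is the total from those that supplied no training data, and is zero only if all of them supplied some.

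The count therefore runs from 0 to 100, which is every possible value. It describes what is unknown and is not a measure of harm. Failure needs every recruiting trust to be a training source, and the protocol does not state this for any trust.

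**3. Is the overfitting half of the standard covered?** Largely. Training patients had a successful ablation (section 3.2), so their pathway location is known. Section 4.3 excludes anyone whose location is known from a previous study. Training patients should therefore not re-enter as test cases, and the lock stops learning from test data. What stays open is generalisability across institutions.

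**4. What depends on the answer?** The primary measure is the proportion of ECGs on which the algorithm matches the operator's recorded location (section 3.2). It is computed in the same way wherever the patient came from. The sample-size statement rests on 93% against 77% accuracy and uses no centre information.

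**5. What would a separate external estimate add?** For illustration, assume an observed accuracy near the pilot's 93%. The 95% Wilson interval is

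(p + z²/2n ± z√(p(1−p)/n + z²/4n²)) / (1 + z²/n), with z = 1.96.

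- n = 100, 93 correct: 86.3% to 96.6%, width 96.6 − 86.3 = 10.3 points.
- n = 30, 28 correct (an assumed external subset): 78.7% to 98.2%, width 98.2 − 78.7 = 19.5 points.

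Such a line would be descriptive. It can be produced from each patient's recruiting trust, with no new data collection.

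**The case for a change.** The strongest case for a change is that the protocol sets this standard itself, calls it essential, carries the other three through and leaves this one without a recruitment route. Where patients come from and where the training data came from are design facts, not matters usually left to an analysis plan. A site list alone would not give the source of the training ECGs, and stating it would take one sentence.

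Much of this stands. The institutional reading of external is the sensible one, sections 1.1, 3.1 and 4.1 do not fit neatly together, and a reader cannot tell from the protocol whether the standard is met.

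What does not stand is the step from unclear to failed. The harm depends on two facts, which trusts recruit and which supplied training ECGs, and the protocol settles neither. The sponsor knows both, and neither can be altered by the trial's results: the training source is fixed at the lock, and the recruiting trust is fixed for each patient. There is little room for the answer to be chosen after the event.

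**Conclusion.** No change to the plan follows. This is a gap in description that those running and analysing the trial can fill from facts on record. Following the protocol as written gives the same primary accuracy estimate from the same 100 patients, whichever way the missing facts fall.

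What varies is the claim that may be attached to the estimate. If some recruiting trusts supplied no training data, the result for their patients bears on generalisability and can be shown separately. If the only recruiting trust supplied none, the whole cohort is external, at one centre. If every recruiting trust supplied training data, the result is a prospective internal validation and should be described as such. Each of these is a matter of reporting.

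The conclusion rests on three assumptions: that external refers to the institution, that the origin of the training and finalisation ECGs is on record, and that each patient's recruiting trust is known. It would change if it were shown that the sole recruiting trust supplied the training data and that the sponsor still meant to claim external validation. The protocol gives no evidence of either.

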#### **3.2 METHODOLOGY**

##### **Data collection**

All data will pseudonymised at the point of collection by the direct care team. Pseudonymised and anonymised data will be securely held password protected computers at Imperial College London (Sponsor). Pseudonymised data will be kept separately from the key that identifies it and separately from data with the patients name, hospital number, address and NHS number. With the consent of the patient and clinical care team medical information such as procedure reports will be obtained. These data will be kept separate from identifiable personal data. All identifiable information will be securely held in NHS Trust computers and will be held in strict compliance to NHS Data Protection and Confidentiality regulation. Patient identifiable information will not be shared from external institutions.

##### **AI algorithm testing**

The AI algorithm has been trained using raw, digital 12-lead ECG data from patients with manifest accessory pathways who underwent successful ablation. The training data was labelled using associated procedure reports, fluoroscopy and electro-anatomical map data. The algorithm will output the location of an accessory pathway (left vs right, anterior vs posterior, septal vs lateral).

At commencement of the prospective validation study, the final AI accessory pathway localisation algorithm will be locked so that it cannot be trained on any new input data. This will be confirmed by an independent researcher. Using a digital 12-lead ECG as the input, the algorithm will output the categorical location of the pathway; this will be provided as a transverse axis location (left, septal, right) and a vertical axis location (anterior, mid, posterior).

Participants who agree to be recruited to the prospective validation study will undergo 12-lead ECG recordings via conventional digital ECG machines and EP recording systems during their EP study. These ECGs will be analysed at Imperial College London, where the AI algorithm will be applied to determine the AI-predicted location. At the time of their EP study, the successful ablation location will be recorded by the operating physician (estimated

from fluoroscopy). The proportion of ECGs correctly predicted by the AI algorithm, matching the operator assessment, will be the primary outcome measure of AI accuracy.

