### **STATISTICS AND DATA ANALYSIS**

We aim to recruit 100 patients to undergo the AI algorithm prospective validation study. Based on retrospective pilot data of our accessory pathway localisation AI algorithm, we determined the accuracy of the AI algorithm to be 93% accurate and the next best manual algorithm prediction to be 77% accurate. Assuming the same accuracy in the prospective study, using a one-way two sample t-test, 91 participants would be needed to provide 90% power at the 5% significance level.

Data and all appropriate documentation will be stored for a minimum of 10 years after the completion of the study, including the follow-up period.

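### Does the unstated match rule for a two-axis output leave the primary accuracy, and the sizing behind it, undefined?

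*Protocol*

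**What the plan says.** Under AI algorithm testing (section 3.2) the protocol states: "The proportion of ECGs correctly predicted by the AI algorithm, matching the operator assessment, will be the primary outcome measure of AI accuracy". The Study Summary and section 3.4 list the same quantity as "Overall accuracy of the AI algorithm predictions, as compared to the operator assessment". None of these places mentions an axis.

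The same subsection describes the output twice. The paragraph on training ends with: "The algorithm will output the location of an accessory pathway (left vs right, anterior vs posterior, septal vs lateral". The next paragraph, on the locked final algorithm, says the output will be given as "a transverse axis location (left, septal, right) and a vertical axis location (anterior, mid, posterior". For the reference, "the successful ablation location will be recorded by the operating physician"; no categories are listed for that record.

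Section 1.1 reports the pilot result as an "accuracy of 93% when retrospectively applied to 156 12-lead ECGs (left vs septal vs right". The statistics section says "we determined the accuracy of the AI algorithm to be 93% accurate and the next best manual algorithm prediction to be 77% accurate" and then: "Assuming the same accuracy in the prospective study, using a one-way two sample t-test, 91 participants would be needed to provide 90% power". It gives no level for either percentage.

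**The concern.** One set of locked predictions could give more than one primary accuracy, depending on whether a correct transverse class is enough or the vertical class must be right too. The stricter rule can never give a higher figure than the transverse rule. If the rule were left open until predictions had been compared with outcomes, the more flattering level could be chosen, which is what a locked, prospective validation is meant to prevent. Sensitivity, specificity, predictive values and F1 depend on the same classes.

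The sizing raises a related worry. A one-axis 93% appears to be carried into a study whose output has two axes, beside a 77% of unknown level. If both axes had to match, the planning value would be too high, or the two percentages might not be comparable.

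**Working it through.** **The planned figure.** Inputs from the statistics section: 93% against 77%, 5% level, 90% power, 91 participants. An unpaired comparison of two proportions needs 84 per group one-sided (96 with continuity correction) and 103 two-sided. A two-sample t-test on 0/1 scores needs 82 or 86 one-sided, depending on the variance used. None of these gives exactly 91. With 91 per group the normal approximation gives 92% power one-sided and 86% two-sided. How 91 was reached is a separate question, and the present point does not depend on it.

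**The two output descriptions.** Read the first, at its most literal, as three crossed two-way labels: 2 × 2 × 2 = 8 combinations. The second has 3 × 3 = 9. On the transverse axis the first collapses into the second: left-lateral becomes left, right-lateral becomes right, and either septal label becomes septal. The real mismatch is the vertical level mid, which only the second has. The second description belongs to the algorithm under test and names axes and levels. The first is a looser list that closes the paragraph on training.

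**The level of the 93%.** Section 1.1 ties 93% of 156 ECGs to left/septal/right, the same three classes as the transverse axis of the second description. If the 77% uses those classes too, the sizing compares like with like.

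**Effect on the primary result if both axes must match.** As an identity,

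both-axes accuracy = transverse accuracy − share with right transverse but wrong vertical class.

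With transverse accuracy 0.93 and vertical accuracy v, and without assuming independence, both-axes accuracy lies between 0.93 + v − 1 and min(0.93, v). No v is given; 0.90 and 0.95 are assumptions.

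| v (assumed) | Lower bound | Upper bound | Drop from 93% |
|---|---|---|---|
| 0.90 | 0.93 + 0.90 − 1 = 0.83 | 0.90 | 3 to 10 points |
| 0.95 | 0.93 + 0.95 − 1 = 0.88 | 0.93 | 0 to 5 points |

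Wilson 95% intervals, assuming 100 scorable ECGs, one per patient:

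| Correct of 100 | 95% interval |
|---|---|
| 93 | 86.3% to 96.6% |
| 90 | 82.6% to 94.5% |
| 88 | 80.2% to 93.0% |
| 83 | 74.5% to 89.1% |

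The half-width grows from 5.2 points at 93% to 7.3 at 83%. The estimate moves, but the study still estimates it with similar precision.

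**Effect on the sized contrast.** AI against manual algorithm is a secondary outcome, so its power is not the power of the primary measure. Suppose for illustration that both planning figures are transverse, that axes err independently, and that the test is unpaired and one-sided with 91 per group.

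- Vertical accuracy 0.90 for both methods: 0.93 × 0.90 = 0.837 against 0.77 × 0.90 = 0.693, power 74%.
- Vertical accuracy 0.95 for the AI and 0.85 for the manual method: 0.93 × 0.95 = 0.884 against 0.77 × 0.85 = 0.655, power 98%.

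Scoring both axes can therefore lower or raise power relative to the 92% above. The real comparison is also paired within patients, with a discordance that is not given. Neither the direction nor the size of any effect can be derived from the protocol.

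**The case for a change.** The strongest argument for acting is that this is more than silence. Two sentences in one subsection each say what the algorithm will output, and they differ. An analysis plan that adopts one would still disagree with the other. A record of right and septal cannot be scored under the second scheme without a mapping, and the protocol states none. Locking the algorithm stops retraining but does not fix the scoring. The remedy would cost only some wording and a look at the pilot data.

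Part of this stands. The vertical labels do differ, and the levels of the 93% and 77% in the statistics section are unstated. Both would be worth tidying if the protocol were being amended anyway.

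The rest carries less weight. The protocol does not say that the first list is a set of crossed labels, and the mapping on the transverse axis is the obvious one. Nothing in the protocol provides for choosing the level after seeing results, and an unseen analysis plan may already settle it. The claim that 93% is an upper bound for a both-axes match is true only of the proof-of-concept algorithm on its 156 retrospective ECGs, or of a planning value carried forward from it. The algorithm to be tested is still to be finalised, so its prospective accuracy is not bounded by that figure.

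**Conclusion.** No change to the plan follows. The inconsistency in the output labels is clerical, and the later, more specific description can govern. The match rule and the coding of the operator's record are details that an analysis plan or case report form commonly supplies; with only the protocol at hand they are not shown to be missing. No stated number is shown to be wrong on this ground.

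If a match on both axes were required, the primary estimate would be 3 to 10 points below 93% at an assumed vertical accuracy of 90%, or 0 to 5 points at 95%, with the interval half-width going from about 5 to at most about 7 points. These ranges assume transverse accuracy stays at 93% and that there are 100 scorable ECGs, one per patient. The sizing is coherent on the transverse reading, provided the 77% uses the same three classes, which the protocol does not state. Anyone reporting a both-axes result should remember that the described 93% is a transverse figure and that the stated power does not carry over to that result.
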